During the hotel phase, all challenged subjects will be assessed on a daily basis in an identical manner. An evaluation will be done each morning (headache, muscle aches, etc.) and blood will be drawn for smear. All challenged subjects will be instructed to check in with clinical staff by telephone call or in-person each evening during the hotel stay until they are positive for malaria. They will be asked if they feel any differently since they were seen in the morning. At any time required, the on-duty investigator will arrange for the timely production of blood smears, along with their examination and interpretation, in order to treat rapidly those subjects in whom therapy for malaria is indicated. Once a positive smear is identified, daily blood films will continue to be obtained until three consecutive films are negative (separated by more than 12 hours). A complete blood count and serum chemistry tests will be done when parasites are initially found in the blood (this could be done on the day of parasitemia detection or the day after).

The maximum hotel stay for malaria-challenged subjects should be approximately 10 days (Day 295 [Visit 16] to Day 304 [Visit 25]). A subject who develops malaria, is treated, and has three consecutive negative malaria smears (separated by more than 12 hours), will not need to remain in the hotel. The investigators will be responsible for accounting for any subjects who do not arrive in the hotel during the challenge phase. If required, the investigators will physically locate and treat any malaria-infected subject who is unable to maintain the follow-up dictated by this study.

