Record any intercurrent medical conditions	•	•	•	•	•	•	•	•	•	•	•	•		•	•
Distribution of diary cards		0	0				0								
Return of diary cards			0			0				0					
Diary card transcription by investigator			•			•				•					
Recording of solicited local and general AEs (Days 0–6) post-vaccination		•	•				•								
Recording of unsolicited AEs (Day 0-29) post-vaccination		•	•	•	•	•	•	•	•						
Recording of AEs (Day 0-29) post-challenge											•	•	•	•	
Recording of SAEs (all, fatal, related) and pregnancies		•	•	•	•	•	•	•	•	•	•	•	•	•	•
Recording of SAEs related to study participation, or to a concurrent GSK medication/vaccine	•	•	•	•	•	•	•	•	•	•	•	•	•	•	•
Recording of all AEs and SAEs leading to withdrawal from further vaccination		•	•	•	•	•	•	•	•	•	•	•	•	•	•
Recording of AEs of specific interest ^f		•	•	•	•	•	•	•	•	•	•	•	•	•	•
Study Conclusion															•

β-HCG: Beta-human chorionic gonadotropin; PBMC: peripheral blood mononuclear cells; Vacc: vaccination.

* Visit 12 = 291, Visit 13 = Day 292, Visit 14 = Day 293, Visit 15 = Day 294, Visit 16 = Day 295, Visit 17 = Day 296, Visit 18 = Day 297, Visit 19 = Day 298, Visit 20 = Day 299, Visit 21 = Day 300, Visit 22 = Day 301, Visit 23 = Day 302, Visit 24 = Day 303, Visit 25 = Day 304, Visit 26 = Day 306, Visit 27 = Day 308, Visit 28 = Day 310, Visit 29 = Day 312.

** A blood sample for biochemistry and hematology parameters will be collected the day of first parasitemia (between Visit 12 [Day 291] and Visit 29 [Day 312]).

*** Blood sample for assessment of parasitemia (blood smear) will be collected daily for 14 days (from Day 291 [Visit 12] to Day 304 [Visit 25]) and then every two days for nine days (Day 306 [Visit 26], Day 308 [Visit 27], Day 310 [Visit 28], Day 312 [Visit 29], and Day 314 [Visit 30]). For subjects who develop malaria, blood smear may be discontinued once the subject has three consecutive negative smears (separated by more than 12 hours) following initial treatment.

CONFIDENTIAL

205081 (MALARIA-092)
Protocol Administrative Change 1 Final

**** Blood sample for assessment of parasitemia (PCR testing) will be collected on the day of subject entry into the hotel (Day 295).

a Including a check of NHANES I criteria and electrocardiogram (see [APPENDIX C](#)).

^b The screening laboratory results (HIV, HCV, HBsAg, ALT, AST, creatinine, hemoglobin, leukocytes [WBC], platelets, and urine β -HCG) must be checked during the screening activities and before randomization.

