4.2.3. Safety

- Safety and reactogenicity of the investigational vaccine for each vaccination schedule:
 - Occurrence of solicited local and general AEs within seven days (day of vaccination and six subsequent days) after each vaccination.
 - Occurrence of unsolicited AEs within 30 days (day of vaccination and 29 subsequent days) after each vaccination, according to the Medical Dictionary for Regulatory Activities (MedDRA) classification.
 - Occurrence of AEs within 30 days (day of challenge and 29 subsequent days) after challenge, according to the MedDRA classification.
 - Occurrence of SAEs (all, fatal, related to investigational vaccine) within 30 days (day of vaccination and 29 subsequent days) after each vaccination, according to the MedDRA classification.
 - Occurrence of SAEs (all, fatal, related to investigational vaccine) during the whole study period (from Dose 1 [Day 0] up to study conclusion [Day 376]), according to the MedDRA classification.
 - Occurrence of AEs and SAEs leading to withdrawal from further vaccination from Dose 1 (Day 0) up to study conclusion (Day 376), according to the MedDRA classification, for each vaccinated subject.
 - Occurrence of pIMDs from Dose 1 (Day 0) up to study conclusion (Day 376), according to the MedDRA classification, for each vaccinated subject.
 - Occurrence of meningitis from Dose 1 (Day 0) up to study conclusion (Day 376), according to the MedDRA classification, for each vaccinated subject.
 - Occurrence of abnormal laboratory values at screening, Day 35, Day 58, Day 203, Day 226, the day of first parasitemia, and Day 314 for each vaccinated subject and at screening, the day of first parasitemia and Day 314 for the infectivity control subjects.

- Safety after sporozoite challenge in the infectivity control group.
 - Occurrence of AEs within 30 days (day of challenge and 29 subsequent days) after challenge, according to the MedDRA classification.
 - Occurrence of SAEs (all, fatal, related) from day of challenge (Day 286) to the end of the challenge phase (Day 314), according to the MedDRA classification.

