The percentage of subjects reporting SAEs (all, fatal, related) occurring within 30 days (day of vaccination and 29 subsequent days) after each dose of study vaccine, classified by the MedDRA preferred term level will be tabulated with exact 95% CI.

The percentage of subjects reporting SAEs (all, fatal, related) occurring from Dose 1 (Day 0) until last study visit (Day 376), classified by the MedDRA preferred term level will be tabulated with exact 95% CI.

The percentage of subjects reporting SAEs (all, fatal, related) occurring from day of challenge (Day 286) to the end of the challenge phase (Day 314), according to the MedDRA classification will be tabulated with exact 95% CI.

Subjects reporting pregnancies will be described.

The percentage of subjects reporting an AE or SAE leading to withdrawal from further vaccination from Dose 1 (Day 0) until last study visit (Day 376), classified by MedDRA preferred term level, will be tabulated with exact 95% CI.

The percentage of vaccinated subjects reporting AEs of specific interest (meningitis and pIMDs) from Dose 1 (Day 0) until last study visit (Day 376), classified by MedDRA preferred term level, will be tabulated with exact 95% CI.

Biochemistry (ALT, AST and creatinine) and hematological (hemoglobin, WBC and platelets) laboratory values will be presented by visit according to toxicity grading scales and tabulated by group.

The normal ranges and toxicity grading for laboratory safety parameters used in this study are presented in [Table 4](#)

Table 4 Toxicity grading scales for blood testing

Adverse event	Intensity grade	Intensity*
Hemoglobin (males)	Normal range	≥12.5 g/dl
	1	< 12.5 but ≥ 11.0 g/dl
	2	< 11.0 but ≥ 10.0 g/dl
	3	< 10.0 g/dl
Hemoglobin (females)	Normal range	≥11.5 g/dl
	1	< 11.5 but ≥ 10.5 g/dl
	2	< 10.5 but ≥ 9.5 g/dl
	3	< 9.5 g/dl
Increase in leukocytes (WBC)	Normal range	≤10799 cells/mm ³
	1	10800 - 15000 cells/mm ³
	2	15001 - 20000 cells/mm ³
	3	> 20001 cells/mm ³
Decrease in leukocytes (WBC)	Normal range	≥3200 cells/mm ³
	1	2500 - 3199 cells/mm ³
	2	1500 - 2499 cells/mm ³
	3	< 1500 cells/mm ³
Decrease in platelets	Normal	≥140000 cells/mm ³
	1	125000 - 139000 cells/mm ³
	2	100000 - 124000 cells/mm ³
	3	< 100000 cells/mm ³
Alanine Aminotransferase	Normal range	Below ULN (60 U/l for males; 40 U/l for females)
	1	1.1 - 2.5 x ULN
	2	2.6 - 5 x ULN
	3	> 5 x ULN
Aspartate Aminotransferase	Normal range	Below ULN (40 U/l for males; 35 U/l for females)
	1	1.1 - 2.5 x ULN
	2	2.6 - 5 x ULN

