Template 23	Summary of subjects with at least one serious related unsolicited adverse event classified by MedDRA Primary System Organ Class and Preferred Term occurring from day of challenge until the end of challenge phase (Day 314) (Intention-to-treat set)	Post-text/ Web disclosure	TAE1SOCPT
Template 27	Listing of SAEs reported from study start to end of the study (Intention-to-treat population)	Post-text	TAE1SAELIST
Template 28	Listing of (S) AEs and solicited symptoms leading to study/treatment discontinuation (Intent to treat set)	Post-text / Web disclosure/	TAE1WITHDR AWAL

Template #	Table / Listing Title	Output destination	Template name
Template 24	Summary of occurrences and subjects with at least one solicited or unsolicited adverse event classified by MedDRA Primary System Organ Class and Preferred Term (excluding the SAEs) occurring within 30 days of any vaccination (Intention-to-treat set)	Web disclosure	TAC1SOCPT
Template 29	Summary of hematology and biochemistry results (Intention-to-treat population)	Post-text/ Web disclosure	TLB1RANGEV SBSL

12.5. Individual data listings:

Reason for non-eligibility (LIE1LIST)

Demography (LDM1DEMOG)

Reason for visit not done (LDS1NOVIS)

Immunogenicity (LIS1LIST)

Vaccine administration (LEC1EXPO)

Reason for vaccine not administered (LEC1NOADM)

Solicited local adverse events (LEC1LOC)

Solicited general adverse events (LEC1GEN)

Concomitant medications (LCM1LIST)

Pregnancy (Specific)

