<Preferred Term 1 (code)>	xxx	xxx	xx.x	xxx	xxx	xx.x
<Preferred Term 2 (code)>	xxx	xxx	xx.x	xxx	xxx	xx.x
...						
<SOC 2 (code)>	xxx	xxx	xx.x	xxx	xxx	xx.x
<Preferred Term 1 (code)>	xxx	xxx	xx.x	xxx	xxx	xx.x
<Preferred Term 2 (code)>	xxx	xxx	xx.x	xxx	xxx	xx.x

Template 25 Summary of subjects by unsolicited event category, <within 30 days of any vaccination/ within 30 days of post-challenge period / from study start to 30 days post-challenge> (Intention-to-treat set)

	<Group 1> N=XXXX				<Group 2> N=XXXX			
	n	%	95% CI		n	%	95% CI	
			LL	UL			LL	UL
At least one unsolicited adverse event	xxx	xx.x	xx.x	xx.x	xxx	xx.x	xx.x	xx.x
At least one serious unsolicited adverse event	xxx	xx.x	xx.x	xx.x	xxx	xx.x	xx.x	xx.x
At least one related unsolicited adverse event	xxx	xx.x	xx.x	xx.x	xxx	xx.x	xx.x	xx.x
At least one serious related unsolicited adverse event	xxx	xx.x	xx.x	xx.x	xxx	xx.x	xx.x	xx.x

Template 26 Listing of potential immune-mediated disorders (pIMDs) reported as identified by predefined list of preferred terms and/or by investigator assessment (Intent to treat set)

Group	Subject number	Gender	Country	Race	Age at onset (Year)	Verbatim Preferred Term	Primary System Organ Class	
xxxxx	xxxxx	xxxxx	xxxxxxx	xxxxxx	xx	xxxxx	xxxxx	
Group	Subject number	Medical visit type	Vaccination	Day of onset	Duration	Intensity Causality	Outcome SAE (Y/N)	pIMD Source
xxxxx	xxxxx	xxxxxxx	xxxxxx	xx	xx	xxxx	xxx	xxxxx

Template 27 Listing of SAEs reported from study start to 28 days post challenge (Intention-to-treat set)

Group	Subject number	Gender	Country	Race	Age at onset (Year)	Verbatim Preferred Term		
xxxxx	xxxxx	xxxxx	xxxxxxx	xxxxxx	xx	xxxxx		
Group	Subject number	Primary System Organ Class	Medical visit type	Vaccination	Day of onset	Duration	Intensity Causality	Outcome
xxxxx	xxxxx	xxxxx	xxxxxxx	xxxxxx	xx	xx	xxxx	xxx

Template 28 Listing of (S) AEs and solicited symptoms leading to study/treatment discontinuation (Intent to treat set)

Group	Subject number	Gender	Country	Race	AE Description	SAE (Y/N) Causality	Outcome	Vaccination and visit
xxxxx	xxxxx	xxxxx	xxxxxxx	xxxxxx	xxxxxx	x	xxxxx	xxxxx
Vaccination: x at visit x								

Template 29 Summary of hematology and biochemistry results (Intention-to-treat set)

Timepoint	Value at timepoint	<Group 1>		<Group 2>	
		N	%	N	%
<Timepoint 1>	N	xxx		xxx	
	Grade 1	xxx	xx.x	xxx	xx.x
	Grade 2	xxx	xx.x	xxx	xx.x
	Grade 3	xxx	xx.x	xxx	xx.x
	Grade 4	xxx	xx.x	xxx	xx.x
	Unknown	xxx	xx.x	xxx	xx.x

[figure not shown]

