N = Number of subjects having received at least one dose
 n/% = Number / percentage of subjects in each category

Template 30 Summary of subjects taking a concomitant medication with <7 days following each vaccination and overall / during challenge phase> (Intent to treat set)

	N	<Group 1>				<Group 2>			
		n	%	95% CI		n	%	95% CI	
				LL	UL			LL	UL
<Vaccination at visit 1>	xxx	xxx			xxx				
Any	xxx	xx.x	xx.x	xx.x	xxx	xx.x	xx.x	xx.x	
Any antipyretic	xxx	xx.x	xx.x	xx.x	xxx	xx.x	xx.x	xx.x	
<Vaccination at visit 2>	...								
...									
Per subject									
Per vaccination									

Template 31 Bar graph of the daily prevalence of <pain/redness/swelling> between day 1 and day 7 following each vaccination (Intent to treat set)

Example:

Template 32 Minimum and maximum dates (intent-to-treat set)

Visit Description	Parameter	<each group> Date	<each group> Date	Overall Date
< each informed consent>	Minimum	DDMMYYYY	DDMMYYYY	DDMMYYYY
	Maximum	DDMMYYYY	DDMMYYYY	DDMMYYYY
[Randomization]	Minimum	DDMMYYYY	DDMMYYYY	DDMMYYYY
	Maximum	DDMMYYYY	DDMMYYYY	DDMMYYYY
<each visit>	Minimum	DDMMYYYY	DDMMYYYY	DDMMYYYY
	Maximum	DDMMYYYY	DDMMYYYY	DDMMYYYY

Short group label = long group label

	
Statistical Analysis Plan	
Detailed Title:	A Phase IIa, open-label, controlled, mono-center study to evaluate the efficacy, immunogenicity and safety of GSK Biologicals' candidate malaria vaccines RTS,S/AS01 _E and RTS,S/AS01 _B administered as various dose schedules according to a 0, 1, 7-month or a 0, 7-month schedule in healthy malaria-naïve subjects aged 18-55 years.
eTrack study number and Abbreviated Title	205081 (MALARIA-092)
Scope:	All data pertaining to the above study.
Date of Statistical Analysis Plan	Final: 24-MAY-2018
Co-ordinating author:	PPD [redacted] (Statistician)
Reviewed by:	PPD [redacted] (Clinical Research and Development Lead) PPD [redacted] (Lead Scientific writer) PPD [redacted] (Scientific writer) PPD [redacted] (Regulatory Affair) PPD [redacted] (SERM physician) PPD [redacted] (SERM Scientist) PPD [redacted] (CLS Manager) PPD [redacted] (Lead statistical analyst) PPD [redacted] (Lead statistician) PPD [redacted] (Public disclosure)
Approved by:	PPD [redacted] (Clinical Research and Development Lead) PPD [redacted] (Lead Scientific writer) PPD [redacted] (Lead statistical analyst) PPD [redacted] (Lead statistician)

APP 9000058193 Statistical Analysis Plan Template (Effective date: 14April 2017)

TABLE OF CONTENTS

	PAGE
LIST OF ABBREVIATIONS	6

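### The laboratory table's footnote uses all dosed subjects as the denominator at every timepoint, which leaves infectivity controls with N = 0 and dilutes vaccine-group percentages, most of all at first parasitemia

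*SAP*

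**What the plan says.** SAP 12.4 lists a single laboratory summary, "Summary of hematology and biochemistry results (Intention-to-treat population"), built on Template 29 and marked for post-text and web disclosure. In SAP 12.6.4 the shell shows, at each timepoint and for each group, an N row, rows for Grades 1 to 4 and a row labelled Unknown. Its two footnotes are "N = Number of subjects having received at least one dose" and "n/% = Number / percentage of subjects in each category".

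SAP 6.5.1 says only that "laboratory values will be presented by visit according to toxicity grading scales and tabulated by group". The table in SAP 11.2.5 that assigns denominators covers concomitant vaccination, solicited general and local symptoms, unsolicited symptoms and concomitant medication. It has no row for laboratory data.

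The endpoint in SAP 4.2.3 is "Occurrence of abnormal laboratory values at screening, Day 35, Day 58, Day 203, Day 226, the day of first parasitemia, and Day 314" for vaccinees. For infectivity controls it is the same outcome at screening, first parasitemia and Day 314.

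On sampling, the footnote to protocol Table 6 (section 6.5) states "A blood sample for biochemistry and hematology parameters will be collected the day of first parasitemia". Protocol 6.4.1.5 gives the trigger: "A complete blood count and serum chemistry tests will be done when parasites are initially found in the blood".

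**The concern.** The footnote suits adverse events, which are collected from everyone dosed. Template 23, an adverse-event table, carries the same sentence. A laboratory grade is different, because a subject without a blood sample cannot be classed as abnormal or normal. Keeping unsampled subjects in the base pulls every percentage down, by an amount that depends on how many were sampled.

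At first parasitemia that number is set by vaccine efficacy. A schedule that protects more people would show fewer laboratory abnormalities even if infected subjects were affected identically in every group. The infectivity controls receive no dose, so under the footnote they have no denominator at all. The outcome is a secondary safety endpoint. The table is publicly disclosed, and SAP 12.5 lists no individual laboratory listing that would correct it.

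**Working it through.** **Inputs** (protocol 11.4 unless stated)
- 26 subjects per vaccine group, at least 20 challenged, about 20% drop-out in vaccinees.
- Planned infections: 19/20 controls and 6/20 vaccinees.
- Efficacy range in the protocol's own power table: 50% to 90%.
- Controls receive no dose but, once challenged, belong to the Intent-To-Treat Set (SAP 2 and 5.1.2).

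**Planning figures reproduced**
- 20/(1 − 0.20) = 25, against the stated 26. Conversely, 26 × 0.80 = 20.8 challenged.
- Efficacy = 1 − (6/20)/(19/20) = 68.4%, against the stated approximate 68%.

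**Formula.** Footnote percentage = (abnormal/dosed) = (abnormal/sampled) × (sampled/dosed). The dilution factor is therefore sampled/dosed, whatever the abnormality rate.

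**First parasitemia, vaccine group of 26 with 20 challenged**

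| Scenario | Infected and sampled | Factor | Prints as, if 50% of sampled are abnormal (assumption) |
|---|---|---|---|
| Plan, 6/20 infected | 6 | 6/26 = 0.23 | 11.5% |
| Efficacy 50% | 0.95 × 0.50 × 20 = 9.5 | 0.37 | 18.3% |
| Efficacy 90% | 0.95 × 0.10 × 20 = 1.9 | 0.07 | 3.7% |
| All 20 infected | 20 | 0.77 | 38.5% |

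The second and third rows have the same true rate among infected subjects, yet they print as 18.3% and 3.7%. That gap comes from the number infected, not from the laboratory findings.

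**Day 314, vaccine group.** With 20 of 26 remaining the factor is 20/26 = 0.77. With 20.8 remaining it is 0.80. Both assume no further loss after challenge.

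**Infectivity controls.** No doses are given, so N = 0 and no percentage can be formed at any of their three timepoints.

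**Search for an override.** SAP 6.5.1 gives no denominator and SAP 11.2.5 has no laboratory row. Template 14, for immunogenicity, bases N on subjects with available results, so the SAP uses that definition where it intends it.

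**Row labels.** SAP Table 4 defines a normal range and Grades 1 to 3. Template 29 prints Grade 4, which is undefined, and has no Normal row.

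**The case against.** **The footnote may be leftover text.** It matches Template 23 word for word, while Template 29 repeats N under each timepoint, which hints at a timepoint-specific count. The safety-template footnotes are not always the governing rule either: Template 21 also bases N on dosed subjects, yet SAP 11.2.5 restricts solicited symptoms to completed symptom screens. This stands as evidence that the intent may differ from the wording. For laboratory data, however, no other text takes over, so the footnote is the only stated rule.

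**The Unknown row.** If unsampled subjects are placed there, the number tested can largely be recovered and no data are lost. That limits the harm. The row is undefined, though, and the percentages beside it would still be on the wrong base.

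**A per-vaccinee rate is legitimate.** The endpoint is worded for each vaccinated subject, and a rate among infected subjects conditions on a post-vaccination outcome. But the documents do not state a per-vaccinee target for the first-parasitemia sample, and an all-dosed base also counts drop-outs who were never challenged.

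**Two stronger readings are not supported.**
- A reader might divide controls by 20 and vaccinees by 26 and infer a false difference of (19/20)/(6/26) = 4.1-fold. Read literally, the footnote gives controls N = 0, so that comparison does not arise. If controls are counted through the Intent-To-Treat Set instead, 4.12 = 3.17 × 1.30. The 3.17 is the assumed infection ratio (0.95/0.30), and only the 1.30 (26/20) comes from counting unchallenged vaccinees.
- A reader might infer that Adu1Fx will be shown as 0% abnormal at Day 35 and Day 58, when it is not sampled. Protocol Table 17 excludes that group at both visits (104 subjects, not 130), and nothing shows that those cells are planned.

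SAP 7 makes all analyses descriptive, and Template 29 has no test or interval. No decision rule depends on it.

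**Conclusion.** The point holds as a wrongly stated denominator in the only laboratory summary table. Applied as written, it gives controls no denominator for a stated endpoint. It also multiplies vaccine-group percentages at first parasitemia by about 0.23 on the planning figures, and by 0.07 to 0.37 across efficacies of 90% to 50%. At Day 314 the factor is about 0.77 to 0.80. These factors assume 26 dosed and 20 challenged per group (20 to 20.8 remaining at Day 314), 95% infection in controls for the efficacy range, and a sample from every parasitemic subject. They do not depend on the abnormality rate; the 50% used above is only for illustration.

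The harm is misleading percentages that cannot be compared between groups, in a descriptive table. The underlying data are intact, and the trial's efficacy conclusions are unaffected.

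**What to change.** In Template 29:

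1. Define N as the number of subjects with an available result for that parameter at that timepoint, in all six groups including infectivity controls, and base the percentages on it.
2. Show subjects without a result as a separate count, outside the percentage base, and define what Unknown means if that row is kept.
3. Label the first-parasitemia rows as describing parasitemic subjects who were sampled.
4. Tabulate only the group-by-timepoint cells scheduled in protocol Table 17, so no Adu1Fx cells at Day 35 or Day 58.
5. Replace the undefined Grade 4 row with a Normal (Grade 0) row.

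A laboratory row in the SAP 11.2.5 denominator table would keep text and shell aligned. The cost is a wording and programming change to one table, with no new data. The downside is a small N at first parasitemia, about 6 per vaccine group on the planning figures and about 2 at 90% efficacy, so counts should be printed beside the percentages.

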Table 2	Intervals between study visits for the investigational vaccine group: Adu1Fx	10
Table 3	Intervals between study visits for the infectivity control group.....	10
Table 4	Toxicity grading scales for blood testing	26

LIST OF FIGURES

	PAGE
Figure 1 Study design	9

LIST OF ABBREVIATIONS

AE	Adverse event
Anti-CS	Antibody to the Plasmodium falciparum circumsporozoite (CS) repeat domain
Anti-HBs	Antibody to the hepatitis B surface antigen
AS01 _B	GSK's proprietary Adjuvant System containing MPL, QS-21 and liposome (50 µg MPL and 50 µg QS-21)
AS01 _E	GSK's proprietary Adjuvant System containing MPL, QS-21 and liposome (25 µg MPL and 25 µg QS-21)
ALT	Alanine aminotransferase
AST	Aspartate aminotransferase
ATP	According-To-Protocol
CDISC	Clinical Data Interchange Standards Consortium
CI	Confidence Interval
CLS	Clinical laboratory sciences
CRF	Case Report Form
C-term	CS terminal portion of the protein
CTRS	Clinical Trial Registry Summary
eCRF	electronic Case Report Form
EPT	Endpoint titer
ES	Exposed Set
EU/ml	ELISA unit per milliliter
GMC	Geometric mean concentration
GSK	GlaxoSmithKline
HBsAg	Hepatitis B surface Antigen
ICH	Internal Conference on Harmonization
IgG	Immunoglobulin G
IU/ml	International units per milliliter
ITTS	Intent-To-Treat Set
LL	Lower Limit of the confidence interval
MedDRA	Medical Dictionary for Regulatory Activities
mIU/ml	Milli International units per milliliter
NP	Not protected
P	Protected

[figure not shown]
PCR	Polymerase chain reaction
PD	Protocol Deviation
pIMD	potential Immune Mediated Disease
PPS	Per-Protocol Set
SAE	Serious adverse event
SAS	Statistical Analysis System
SAP	Statistical Analysis Plan
SD	Standard Deviation
SERM	Safety Evaluation and Risk Management
SHS	Study Headline Summary
TFL	Tables Figures and Listings
TOC	Table of Content
UL	Upper Limit of the confidence interval
ULN	Upper Limit of normal range
VE	Vaccine Efficacy
WBC	White blood cells

